3.1 Primary objectives and endpoints

Primary objective 1:

To evaluate the safety and tolerability of the following regimens in healthy adults:

- Adjuvanted FP conjugate vaccine administered IM at a dose of 25 or 200 mcg,
- Adjuvanted Trimer 6931, administered IM at a dose of 100 or 200 mcg,
- Adjuvanted Trimer 4571 administered IM at 200 mcg, or
- Prime-boost vaccination regimen of FP conjugate and Trimer 4571.

Primary endpoint 1:

Local and systemic reactogenicity signs and symptoms, laboratory measures of safety, and adverse and serious adverse events.

SAEs, medically attended adverse events (MAAEs), adverse events of special interest (AESIs) and AEs leading to early participant withdrawal or permanent discontinuation which will be collected throughout the study and for 12 months following any receipt of study product. Additionally, all adverse events will be collected for 28 days after any receipt of study vaccination. All safety lab related adverse events will be collected throughout duration of study.

Primary objective 2:

To evaluate the ability of FP-conjugate and Trimer 4571 vaccines to elicit FP-specific binding antibodies in Part B participants.

Primary endpoint 2:

Magnitude and response rate of serum antibody binding of FP and envelope trimer antigens as measured by the MSD assay 2 weeks after the last vaccination.

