9.1 Adverse events

Unsolicited AEs will be collected over a period of 28 days after each vaccination. All collected AEs are captured in the clinical database on the appropriate case report form (CRF). Clinic staff should evaluate every AE to determine if (1) the AE meets the requirements for expedited reporting (see Section 9.2.1), (2) if the AE meets the criteria for a safety pause/prompt AE review (see Section 9.5), (3) if the AE meets the criteria for an MAAE, and (4) if the AE is a potential immune-mediated medical condition (PIMMC) or an AESI. A sample list of AESIs and PIMMCs is provided in [Appendix M](#).

In addition, a limited set of AEs will be collected and reported for 12 months following any vaccine administration.

- SAEs/EAEs,
- AESIs,
- MAAEs (defined as any AEs leading to an unscheduled visit to a healthcare professional),
- Safety lab-related AEs,
- AEs leading to early participant withdrawal or early discontinuation of study vaccine(s) administration.

AEs will be graded according to the Division of AIDS (DAIDS) Table for Grading the Severity of Adult and Pediatric Adverse Events, Corrected Version 2.1 (<https://rsc.niaid.nih.gov/clinical-research-sites/daids-adverse-event-grading-tables>), with the following exceptions:

- Unintentional Weight Loss is required to be reported as an AE only if it is considered to be potentially deleterious to the participant's health (see HVTN 303 SSP).
- Creatinine is required to be reported as an AE only if it is gradable per the increase from local lab ULN parameter. Do not grade elevated creatinine based on the change from the baseline parameter.
- Do not grade creatinine clearance or estimated glomerular filtration rate (eGFR) based on the change from the baseline parameter. Do not grade on the basis of eGFR if there is clinical concern for kidney injury.

- Injection Site Erythema or Redness and Injection Site Induration or Swelling will not consider surface area and interference with usual social and functional activities, such that:
 - Grade 1 is: 2.5 to < 5 cm in diameter;
 - Grade 2 is: ≥ 5 to < 10 cm in diameter;
 - Grade 3 is: ≥ 10 cm in diameter OR Ulceration OR Secondary infection OR Phlebitis OR Sterile abscess OR Drainage;
 - Grade 4 is: Potentially life-threatening consequences (eg, abscess, exfoliative dermatitis, necrosis involving dermis or deeper tissue)

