Appendix F Follow up visit windows post termination of vaccination

Visit windows for Part A (Groups 1-5)						
Visit Number	Visit Type	Lower Allowable Window (-)	Lower Target Window (-)	Target Day*	Upper Target Window (+)	Upper Allowable Window (+)
01	Screening	-56	-	0	-	+0
02	Enrollment/Vaccination 1	-	-	0	-	-
03	1-week post-vaccination 1	-2	-1	7	+1	+3
04	2 weeks post-vaccination 1 Primary Immunogenicity	-4	-2	14	+2	+7
05	Follow-up	-7	-2	28	+2	+7
06	Follow-up	-7	-3	56	+3	+7
07	Follow-up	-7	-3	84	+3	+7
08	Follow-up	-14	-3	112	+3	+14
09	Follow-up	-14	-7	168	+7	+14
10	Follow-up	-14	-7	224	+7	+14
11	Follow-up	-14	-7	280	+7	+14
12	Final Visit	-21	-14	364	+14	+21

* All target dates are relative to Day 0.

Visit windows for Part B (Group 6)						
Visit Number	Visit Type	Lower Allowable Window (-)	Lower Target Window (-)	Target Day*	Upper Target Window (+)	Upper Allowable Window (+)
100	Screening	-56	-	0	-	+0
101	Enrollment/Vaccination 1	-	-	0	-	-
102	1-week post-vaccination 1	-2	-1	7	+1	+3
103	2 weeks post-vaccination 1	-4	-2	14	+2	+14
110	Follow-up visit	-14	-3	84	+3	+14
111	Follow-up visit	-2	-1	91	+1	+3
112	Follow-up visit	-4	-2	98	+2	+14
116	Follow-up visit	-21	-3	168	+3	+21
117	Follow-up visit	-2	-1	175	+1	+3
118	Follow-up visit	-4	-2	182	+2	+14
122	Follow-up visit	-21	-3	252	+3	+21
123	Follow-up visit	-2	-1	259	+1	+3
124	Follow-up visit	-4	-2	266	+2	+14
129	Follow-up visit	-21	-3	336	+3	+21
130	Follow-up visit	-2	-1	343	+1	+3
131	Follow-up visit	-4	-2	350	+2	+14
132	Follow-up visit	-28	-3	392	+3	+28

*Target dates are relative to Day 0 (Enrollment), with the exception of post-vaccination visits, which are relative to the prior vaccination visit.

Visit windows for Part B (Group 7)						
Visit Number	Visit Type	Lower Allowable Window (-)	Lower Target Window (-)	Target Day*	Upper Target Window (+)	Upper Allowable Window (+)
100	Screening	-56	-	0	-	+0
101	Enrollment/Vaccination 1	-	-	0	-	-
102	1-week post-vaccination 1	-2	-1	7	+1	+3
103	2 weeks post-vaccination 1	-4	-2	14	+2	+7
104	Vaccination 2	-6	-3	28	+3	+7
105	1-week post-vaccination 2	-2	-1	35	+1	+3
106	2 weeks post-vaccination 2	-	-2	42	+2	-
107	Follow-up visit	-6	-3	56	+3	+7
108	Follow-up visit	-2	-1	63	+1	+3
109	Follow-up visit	-	-2	70	+2	-
110	Follow-up visit	-6	-3	84	+3	+14
111	Follow-up visit	-2	-1	91	+1	+3
112	Follow-up visit	-4	-2	98	+2	+14
116	Follow-up visit	-21	-3	168	+3	+21
117	Follow-up visit	-2	-1	175	+1	+3
118	Follow-up visit	-4	-2	182	+2	+14
122	Follow-up visit	-21	-3	252	+3	+21

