123	Follow-up visit	-2	-1	259	+1	+3
124	Follow-up visit	-4	-2	266	+2	+14
129	Follow-up visit	-21	-3	336	+3	+21
	Leukapheresis	Leukapheresis (or large blood draw) must be completed at only one of the following visits (130, 131, or 132) but NOT at all 3 visits for the subset of participants who received two vaccinations (see Section 8.4).				
130	Follow-up visit	-2	-1	343	+1	+3
131	Follow-up visit	-4	-2	350	+2	+14
132	Follow-up visit	-28	-3	392	+3	+28

*Target dates are relative to Day 0 (Enrollment), with the exception of post-vaccination visits, which are relative to the prior vaccination.

Visit windows for Part B (Group 8)						
Visit Number	Visit Type	Lower Allowable Window (-)	Lower Target Window (-)	Target Day*	Upper Target Window (+)	Upper Allowable Window (+)
100	Screening	-56	-	0	-	+0
101	Enrollment/Vaccination 1	-	-	0	-	-
102	1-week post-vaccination 1	-2	-1	7	+1	+3
103	2 weeks post-vaccination 1	-4	-2	14	+2	+7
104	Vaccination 2	-6	-3	28	+3	+7
105	1-week post-vaccination 2	-2	-1	35	+1	+3
106	2 weeks post-vaccination 2	-	-2	42	+2	-
107	Follow-up visit	-6	-3	56	+3	+7
108	Follow-up visit	-2	-1	63	+1	+3
109	Follow-up visit	-4	-2	70	+2	+14
113	Follow-up visit	-14	-3	140	+3	+14
114	Follow-up visit	-2	-1	147	+1	+3
115	Follow-up visit	-4	-2	154	+2	+14
119	Follow-up visit	-21	-3	224	+3	+21
120	Follow-up visit	-2	-1	231	+1	+3
121	Follow-up visit	-4	-2	238	+2	+14
122	Follow-up visit	-7	-2	252	+2	+7
125	Follow-up visit	-7	-3	280	+3	+7
126	Follow-up visit	-21	-3	308	+3	+21
127	Follow-up visit	-2	-1	315	+1	+3
	Leukapheresis	Leukapheresis (or large blood draw) must be completed at only one of these 2 visits (128 or 132) but NOT both visits for the subset of participants who received two vaccinations (see Section 8.4).				
128	Follow-up visit	-4	-2	322	+2	+14
132	Follow-up visit	-28	-4	392	+4	+28

*Target dates are relative to Day 0 (Enrollment), with the exception of post-vaccination visits, which are relative to the prior vaccination visit.

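### At the allowable limits of the Appendix F windows, scheduled safety follow-up can end before the 12 months after any dose stated in primary endpoint 1

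*Protocol*

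**What the plan says.** **The collection period.** Protocol 3.1 defines primary endpoint 1 to include SAEs, MAAEs, AESIs and AEs leading to withdrawal or discontinuation, collected "throughout the study and for 12 months following any receipt of study product". SAP section 4 repeats this. Protocol 9.1 agrees: "a limited set of AEs will be collected and reported for 12 months following any vaccine administration".

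**The visits that should deliver it** (Appendix F; columns are lower allowable, lower target, target day, upper target, upper allowable):

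- Part A, last visit: "12 Final Visit -21 -14 364 +14 +21". The footnote reads "All target dates are relative to Day 0".
- Group 7, last visit: "132 Follow-up visit -28 -3 392 +3 +28" (Group 6 has the same row).
- Group 8, last visit: "132 Follow-up visit -28 -4 392 +4 +28".
- Groups 7 and 8, second dose: "104 Vaccination 2 -6 -3 28 +3 +7".
- Part B footnote: "Target dates are relative to Day 0 (Enrollment), with the exception of post-vaccination visits". Visit 132 is labelled a follow-up visit, so it counts from enrolment and does not move with a late second dose.

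**After the last visit.** Appendices B and D schedule no later check for AESIs, MAAEs or SAEs. Protocol 9.2.1 describes only SUSAR reporting after study completion, when staff learn of an event passively.

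All of this is current text: Section 3 was revised for Version 2.0, and Appendix F is new in it.

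**The concern.** The endpoint counts 12 months from any dose. The last visit counts from enrolment and has a wide lower allowance: 28 days in Part B and 21 in Part A. A participant can be inside every allowable window and still have a last scheduled safety check before the 12 months are over. Passive SUSAR reporting would not pick up a medically attended event or a non-serious AESI in the gap.

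Vaccination was stopped on safety grounds, so the length of safety follow-up is something readers of the final report will look for. The deepest possible gap is in the two-dose participants of Groups 7 and 8. It would also be hard to see, because the tables, listings and figures in SAP section 11 include no summary of days followed after the last dose. Someone who finished early but in window would look like a full completer.

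An early Visit 132 is not far-fetched for these participants. Appendix F lets leukapheresis or the large blood draw take place at that visit, and Protocol 8.4 places leukapheresis at 10 months plus or minus 2 after the last vaccination. If it is done at Visit 132, that visit comes no later than about 12 months after dose 2. Earlier visits may be used instead, so this does not apply to everyone.

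**Working it through.** **The plan's own figures.** Protocol 1.6 gives 52 weeks for Part A and 56 weeks for Part B: 52 × 7 = 364 and 56 × 7 = 392. Both match the Appendix F target days. With dose 2 on its target day, 392 − 28 = 364 days. The nominal schedule therefore gives 52 weeks after the last dose in both parts.

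**Formula.** Shortest scheduled follow-up = (last-visit target − lower allowance) − (dose target + upper allowance).

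**Part B, two doses** (11 people: 5 in Group 7, 6 in Group 8). Earliest Visit 132: 392 − 28 = Day 364. Allowable dose 2: Days 28 − 6 = 22 to 28 + 7 = 35.

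| Dose 2 | Visit 132 | Days after dose 2 | Short of 365 |
|---|---|---|---|
| Day 35 | Day 364 | 364 − 35 = 329 | 36 |
| Day 28 | Day 364 | 364 − 28 = 336 | 29 |
| Day 22 | Day 364 | 364 − 22 = 342 | 23 |
| Day 35 | Day 392 | 392 − 35 = 357 | 8 |
| Day 28 | Day 392 | 392 − 28 = 364 | 1 |

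Within the narrower target windows the minimum is (392 − 3) − (28 + 3) = 358 in Group 7 and (392 − 4) − 31 = 357 in Group 8.

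**Part B, one dose.** 392 − 28 − 0 = 364 days at minimum, so there is no material shortfall.

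**Part A** (15 people, one dose at Day 0). 364 − 21 = Day 343, which is 22 days short of 365. The target-window limit is 364 − 14 = Day 350; on target it is Day 364.

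**Definition of 12 months.** The documents do not give it in days. Read as 52 weeks (364 days), the worst gaps are 364 − 329 = 35 and 364 − 343 = 21 days instead of 36 and 22.

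**Other anchor.** If Visit 132 were counted from the actual date of dose 2, its target would be 364 days after that dose and its lower limit 364 − 28 = 336. Re-anchoring alone does not close the gap.

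**The case against.** The strongest reply is that the design is right and only the tolerances are loose. Fifty-six weeks is dose 2 plus 52 weeks, so the nominal schedule was evidently built to cover the period. That stands. A reader might infer that a participant who keeps exactly to schedule leaves early. The documents do not support this: on target both parts give 364 days, and the one-day difference from 365 is a matter of convention.

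The 329-day figure is also a corner case. It needs the latest allowable dose 2 and the earliest allowable Visit 132 in the same person. The windows are symmetric, so visits may equally run late. No visit dates are given, and the number who fell short could be zero. That stands too; 11 and 15 are ceilings.

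A reader might further infer that the shortfall falls mostly on two-dose participants. By headcount Part A is larger (15 against 11), and the worst-case totals are not far apart: 11 × 36 = 396 person-days against 15 × 22 = 330. The two-dose gap is deeper, but it does not affect more people.

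Nor do the documents support saying that the trial's safety evidence as a whole is in doubt. Reactogenicity, 28-day AEs and the scheduled safety labs are untouched. At most about the last five weeks of a limited AE set are exposed, and the planned AE summaries are participant counts.

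Finally, a visit window is not a collection limit: 3.1 and 9.1 state the obligation directly, and 8.2 allows remote visits. The Study Specific Procedures, which are not available here, might specify a closing contact. This softens the conflict but does not remove it, because the protocol's own schedules end at these visits.

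**Conclusion.** The inconsistency is real, and it is minor. The stated period is 12 months after any dose. The allowable windows permit scheduled follow-up to end up to 36 days early for two-dose participants in Groups 7 and 8, and up to 22 days early in Part A. It does not affect one-dose Part B participants, and it is not an error in the nominal schedule.

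This rests on three things: 12 months taken as 365 days (each gap is one day smaller at 364), Visit 132 counted from enrolment as the footnote reads, and no closing contact specified outside the protocol. The extent in practice cannot be judged without actual visit dates.

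**What to change.** Reconcile Protocol 3.1 and 9.1 and SAP section 4 with Appendix F, and define 12 months in days.

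- **Part B.** Anchor the last safety contact to each participant's last vaccination and remove its lower allowance, so that it falls no earlier than 12 months after that dose. At 365 days this means Day 28 + 365 = 393 for an on-target dose 2, or Day 35 + 365 = 400 for the latest one. Both lie inside the present upper limit of 392 + 28 = Day 420. Under 8.2 the contact can be remote and separate from the leukapheresis or large-draw visit, so that collection keeps its own window. This was still feasible for everyone: Part B enrolment began on November 3, 2022, so the earliest in-window Visit 132 was November 2, 2023, after Version 2.0 (September 21, 2023).
- **Part A.** Some windows had already closed. The first participant, enrolled on August 15, 2022, passed Day 385 (364 + 21) on September 4, 2023. Add a remote contact where still possible; otherwise state the endpoint for Part A as collection through the final visit.
- **Reporting.** In the final safety report, give days of follow-up after the last dose by arm (median, minimum, and number below 12 months).

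The cost is a short remote contact for a few participants, an edit to the windows or the endpoint text, and one table row.

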HIV VACCINE
TRIALS NETWORK

PROTOCOL

HVTN 303

A Phase 1, Open-Label Clinical Trial to Evaluate Safety, Tolerability, and Immunogenicity of Adjuvanted HIV-1 Fusion Peptide Conjugate Vaccine (VRC-HIVVCP0108-00-VP) Alone or in Prime-Boost Regimens with Adjuvanted HIV-1 Envelope Trimer 4571 (VRC-HIVRGP096-00-VP) and HIV-1 Trimer 6931 (VRC-HIVRGP0106-00-VP) Vaccines in Healthy Adults

DAIDS DOCUMENT ID 38835

IND 028412 HELD BY DAIDS

CLINICAL TRIAL SPONSORED BY

Division of AIDS (DAIDS)
National Institute of Allergy and Infectious Diseases (NIAID)
National Institutes of Health (NIH)
Department of Health and Human Services (DHHS)
Bethesda, Maryland, USA

STUDY PRODUCTS PROVIDED BY

Vaccine Research Center (VRC)
NIAID, NIH, DHHS
Bethesda, Maryland, USA

September 21, 2023

Final
HVTN 303
Version 2.0

HVTN 303 enrolled (vaccinated) its first participant on August 15, 2022, with the goal to enroll 60 participants in the study. As of Dec 20, 2022, 44 participants were enrolled (no enrollments occurred after this date). Part A (Groups 1, 2, 3, 4, and 5) completed enrollment of 15 participants from August 15 to October 14, 2022.

Part B enrolled 29 participants from November 3 to December 20, 2022: Group 6 enrolled 10 ppts, all of whom received 1 vaccination; Group 7 enrolled 10 participants, 5 of whom received 2 vaccinations; Group 8 enrolled 9 participants, 6 of whom received 2 vaccinations. No participants received a 3rd vaccination.

Over time, the PSRT observed trends in local and systemic reactogenicity (grade 3 fever, grade 3 injection site erythema, and/or induration/swelling), unsolicited adverse events (urticaria, rash, and serum sickness), and temporary increases in absolute eosinophil counts (AECs) post-vaccination. Certain of these events resulted in pauses in all vaccinations, and the PSRT requested the HVTN Safety Monitoring Board (SMB) perform an ad hoc review of all safety data. Following this review on January 11, 2023, the SMB recommended that all vaccinations in the study be permanently discontinued, and that participants be continued in safety follow-up, and these recommendations were implemented.

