2.6 Assessment of Immunogenicity

Vaccinations were stopped on January 13, 2023, resulting in most (33) participants receiving only 1 vaccination and eleven participants in Groups 7 and 8 receiving 2 vaccinations. Specimens to evaluate immunogenicity were collected at baseline and at the specified timepoints after the administration of product until March 13, 2023, when the FDA informed DAIDS that the IND has been placed on Clinical Hold and confirmed that all protocol-related activities must cease except for any participant safety follow-up assessments. The primary immunogenicity time point, after the changes to the vaccination and collection schedule, remains 2 weeks after the last vaccination, however participants only received 1 or 2 vaccinations. Antibody titers will be measured by Electrochemiluminescence (ELICA) using a Meso Scale Discovery (MSD) platform for all participants with one or two vaccinations in Groups 5, 6, 7 and 8.

Additional exploratory assays to assess humoral and cellular immune responses may be performed, including B cell response and neutralization antibody assays.

A specimen collection has been added at approximately 10 months post the

Specimens to evaluate immunogenicity will be collected at baseline and at specified time points throughout the study after the administration of product. HIV-specific humoral immune responses will be assessed by neutralization antibody assays. The primary immunogenicity time point is 2 weeks after the last vaccination.

Trimer 4571- and Trimer 6931-specific antibody titers will be measured by Electrochemiluminescence (ELICA) using a Meso Scale Discovery (MSD) platform. Other exploratory assays to assess humoral and cellular immune responses may be performed with stored samples.

Measurements of antibody, B-cell and T-cell responses may be assessed from stored samples for timepoints throughout the study as exploratory evaluations. This includes a number of high-throughput functional assays and high-throughput biophysical profiling tools to comprehensively characterize the humoral immune response elicited by vaccination regimens.

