2.11.4 Benefits

Study participants will not receive direct health benefit from study participation. Others may benefit from knowledge gained in this study that may aid in the development of an HIV vaccine. The investigational vaccine is not expected to provide protection from HIV infection.

Participants may benefit from more frequent counseling, laboratory tests and physical exams while enrolled in the study. Participants may also experience positive social impacts as a benefit of study participation. When asked, participants say that being in a study made them feel good about helping others, increased their knowledge about HIV, and improved their self-esteem.

3 Objectives and endpoints

On January 13, 2023, a protocol memo was distributed informing the clinical research sites that all vaccinations in HVTN 303 were permanently discontinued. Due to permanent discontinuation of vaccinations, none of the participants received Trimer 6931 in prime-boost regimen. Collection of immunogenicity samples was stopped on March 13, 2023. Sections 2.6 and 3 are the revised version of the original protocol (v1.0) as per the availability of the samples and the content of the current protocol version 2.0.

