6.2.1 Sample size calculations for immunogenicity

The main goals of this trial regarding immunogenicity outcomes involve assessing the ability of FP-conjugate and Trimer 4571 vaccines alone or co-administration to elicit antibody binding FP and envelop trimer antigens and mapping FP-specific serum neutralizing activity induced by the prime vaccines regimens in Groups 5-8 and prime boost vaccines regimens in Groups 7-8. No adjustment for multiple comparisons will be made for the use of multiple assays. The precision with which the true response rate can be estimated from the observed data depends on the true underlying response rate and the sample size. Two-sided 95% CIs for the response rate based on observing a particular rate of responses in the vaccinees is shown in [Table 6-3](#). Calculations are done using the score test method (52). The sample size of n = 13 (Groups 5-6) and n=9 for each of Groups 7 and 8 will be used to evaluate the immunogenicity post the 1st vaccination induced by the vaccination; the sample sizes of n=4, 5 for Groups 7-8 will be used to evaluate the immunogenicity post the 2nd vaccination.

Table 6-3 Two-sided 95% confidence intervals for the true response rate based on observing a particular rate of responses in the vaccinees (n =4, 5, 9, 13)

No. of responses	Observed response rate (%)	95% Confidence interval
2/4	50	[15, 85]
4/4	100	[51, 100]
2/5	40	[11.8, 76.9]
4/5	80	[37.6, 96.4]
3/9	33.3	[12.1, 64.6]
6/9	66.7	[35.4, 87.9]
9/9	100	[70.1, 100]
3/13	23.1	[8.2, 50.3]
6/13	46.2	[23.2, 70.9]
9/13	69.2	[42.4, 87.3]

As shown in [Table 6-4](#), there is limited power for a formal comparison of immunogenicity response rates between Group 7 (n=9) and Group 8 (n=9). For either 80% or 90% power, the sizes of differences that the trial is powered to detect are fairly large. These calculations use a Fisher exact 2-sided test with a type I error rate of 0.05.

Table 6-4 Power for comparison of response rates between 2 arms (n1 = 9, n2 = 9)

True response rate Arm 1 (%)	Minimum true response rate in Arm 2 in order to detect a difference	
	80% power	90% power
10	83	91
20	92	99
30	99	

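### Primary endpoint 2 is timed from the last vaccination, so after the early stop it pools post-dose-1 and post-dose-2 samples in Groups 7 and 8, while Section 6.2.1 keeps the two doses apart

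*Protocol*

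**What the plan says.** Primary objective 2 (Protocol Section 3.1) asks whether the FP conjugate and Trimer 4571 vaccines elicit FP-specific binding antibodies in Part B. It is not comparative. Its endpoint is the response rate and magnitude of "antibody binding of FP and envelope trimer antigens as measured by the MSD assay 2 weeks after the last vaccination".

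Section 2.6 repeats the timing and acknowledges the early stop: the primary time point "remains 2 weeks after the last vaccination, however participants only received 1 or 2 vaccinations". It describes the stop as "resulting in most (33) participants receiving only 1 vaccination and eleven participants in Groups 7 and 8 receiving 2 vaccinations". This is current text. The introduction to Section 3 states that "Sections 2.6 and 3 are the revised version of the original protocol (v1.0) as per the availability of the samples".

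The version 2.0 summary that follows the title page gives the split: "Group 7 enrolled 10 participants, 5 of whom received 2 vaccinations; Group 8 enrolled 9 participants, 6 of whom received 2 vaccinations". All 10 participants in Group 6 had one vaccination.

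Section 6.2.1, also revised for version 2.0, is organized by dose number. For the first dose it uses n=13 for Groups 5 and 6 together, and "n=9 for each of Groups 7 and 8 will be used to evaluate the immunogenicity post the 1st vaccination". For the second dose, "the sample sizes of n=4, 5 for Groups 7-8 will be used to evaluate the immunogenicity post the 2nd vaccination". Table 6-3 gives precision at n = 4, 5, 9 and 13. Tables 6-4 and 6-5 give Group 7 v Group 8 power at 9 v 9.

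Section 6.5.4.1 analyzes Part B participants as randomized, whatever number of injections they had. It tabulates response rates at each assessed timepoint and tests arms at a specific timepoint, but does not say which timepoint is primary. The SAP supplied covers safety only (SAP Section 2).

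**The concern.** When every participant was to complete a full regimen, the last vaccination marked the same point in the regimen for everyone in an arm. After the stop it does not. In Groups 7 and 8 it is dose 1 for some participants and dose 2 for others.

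Two things follow. First, a single response rate or mean magnitude on the stated rule averages two exposures, in proportions set by when vaccination happened to stop, and estimates the response to neither. Secondly, the endpoint in Sections 2.6 and 3.1 is not the quantity for which Section 6.2.1 gives precision and power.

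If the same values were carried into the exploratory between-regimen comparison (Section 3.2, exploratory objective 3), differences between arms would partly reflect number of doses. Some of that is built into the schedule: dose 2 was due at week 4 in Groups 7 and 8 but at week 12 in Group 6.

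**Working it through.** **1. Reproduce the plan's own figures.** The 95% score interval for x/n, with p = x/n and z = 1.96, is [p + z²/2n ± z√(p(1−p)/n + z²/4n²)] / (1 + z²/n). It reproduces all ten rows of Table 6-3, for example 6/9: 35.4 to 87.9%. The table is sound for the sample sizes it uses.

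**2. Does 9 v 9 fit the last-dose definition?** Inputs: the version 2.0 summary and Section 6.2.1.

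- Group 7: 10 enrolled − 5 with two doses = 5 with one dose. Nine post-dose-1 samples must therefore include at least 9 − 5 = 4 from people whose last vaccination was dose 2.
- Group 8: 9 enrolled − 6 with two doses = 3 with one dose. Nine post-dose-1 samples are the whole group, including all 6 with two doses.
- Check: 5 + 6 = 11 two-dose participants, as in Section 2.6.

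So the 9 v 9 set is the post-dose-1 set and cannot be the last-dose set.

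**3. Size of the last-dose set.** I read the post-dose-2 counts of 4 and 5 in group order, and do not substitute a dose-1 sample for a missing dose-2 sample.

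| Group | Post-dose-2 | One-dose participants sampled | Last-dose n | Share post-dose-2 (w) |
|---|---|---|---|---|
| 6 | 0 | 10 | 10 | 0 |
| 7 | 4 | 4 or 5 | 8 or 9 | 4/8 = 0.500 or 4/9 = 0.444 |
| 8 | 5 | 3 | 8 | 5/8 = 0.625 |

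Group 7 has two values because one of its ten post-dose-1 samples is absent and the documents do not say whose. With the counts reversed, Group 8 has 4 + 3 = 7, so 8 is its maximum either way.

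**4. What pooling does to the summary.** Pooled rate = p1 + w(p2 − p1), where p1 and p2 are the response rates after doses 1 and 2. The excess over p1 is w × gain. The documents give no gain, so these are assumed values, in percentage points.

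| Assumed gain | Group 6 | Group 7 | Group 8 | Shift in Group 8 − Group 7 |
|---|---|---|---|---|
| 0 | 0 | 0 | 0 | 0 |
| 20 | 0 | 8.9 to 10 | 12.5 | 2.5 to 3.6 |
| 40 | 0 | 17.8 to 20 | 25 | 5.0 to 7.2 |
| 60 | 0 | 26.7 to 30 | 37.5 | 7.5 to 10.8 |

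The last column is (w8 − w7) × gain, with w8 − w7 = 0.125 or 0.181. A 60-point gain is possible only if p1 is 40% or less.

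**5. Does the smaller count matter in itself?** Hardly. The score interval for 5/8 is 30.6 to 86.3%, against 35.4 to 87.9% for 6/9. Simulated power of the exact two-sided Wilcoxon test at 0.05 (normal data, difference 1.5 SD, all responders, no dose mixing, 20,000 runs) is 79.8% at 9 v 9, matching the 80% entry in Table 6-5, then 78.7% at 9 v 8 and 76.9% at 8 v 8.

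**6. What each dose could support alone.** Post-dose-1 gives 9 v 9, as planned. Post-dose-2 gives 4 v 5: power at 1.5 SD is about 37%, and a difference of about 2.6 SD is needed for 80%.

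**The case against.** The strongest reply is that the endpoint is defined. Each participant has one last vaccination, and Section 2.6 keeps that rule while stating that people had one or two doses. With analysis as randomized regardless of injections received, it can be read as a summary of the regimen as delivered. This stands: a reader might infer that the primary result is undefined, and the documents do not support that. What fails is the meaning of the group-level number and its match to Section 6.2.1.

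Next, the per-dose results are already planned. Section 6.2.1 evaluates each dose, Section 6.5.4.1 tabulates by timepoint, and visits 103 and 106 are separate visits. No passage makes a pooled number the only output. This also stands and limits the harm: the issue is which result carries the primary label.

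A reader might also infer that the planned arm comparisons are biased or underpowered. Neither is shown. Objective 2 is not comparative, comparison between regimens is exploratory, and nothing requires it to use pooled values. The Group 8 − Group 7 shift would be 2.5 to 10.8 points for gains of 20 to 60, against an interval 52.5 points wide at 6/9 (87.9 − 35.4). Section 6.2.1 itself calls power limited.

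Finally, the protocol leaves several immunogenicity choices to a SAP, and the one supplied is for safety. A separate plan may name the dose. Even so, Sections 2.6 and 3.1 would still differ from 6.2.1.

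**Conclusion.** The point holds as an inconsistency within the current protocol, worth correcting. On the stated rule the primary summary mixes one-dose and two-dose samples in Groups 7 and 8 and does not correspond to the precision and power tables. That mismatch follows from the enrollment and dose counts alone, and needs no assumption about immune response.

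The numerical effect is unknown. It is zero if dose 2 adds nothing. Under assumed gains of 20 to 60 points, the pooled rate exceeds the dose-1 rate by 9 to 30 points in Group 7 and by 12.5 to 37.5 in Group 8. Those figures read the counts 4 and 5 in group order; reversed, they become about 10 to 33 and 11 to 34. Group 6 is unaffected. The problem is what the primary number means, not its precision. The absence of an n=8 row in Table 6-3, and of a primary-visit label in the Part B tables of Appendix F, is cosmetic.

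**What to change.** In Sections 2.6, 3.1 and 6.5.4.1, restate primary endpoint 2 by dose number so that it agrees with Section 6.2.1:

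- **Primary result:** MSD binding magnitude and response rate two weeks after the first vaccination (visit 103), for each of Groups 6, 7 and 8. Group 5 (visit 04) is added to Group 6 only for the n=13 estimate in Section 6.2.1. Any exploratory between-arm comparison uses this timepoint.
- **Separate descriptive summary:** the same measures two weeks after the second vaccination (visit 106; n=4 and 5), for Groups 7 and 8 only, not pooled with dose 1.

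Carry the same definition into any immunogenicity SAP. The cost is wording; no new samples or assays are needed. The downside is that dose-2 data leave the between-arm tests, where 4 v 5 could support little.
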